### **5.1.3 Subject Withdrawal Criteria**

Procedures for handling subjects who are discontinued from the trial are described in Section 13.2. Subjects who are discontinued will not be replaced.

## **6. TEST ARTICLES AND REGIMEN**

### **6.1 Description**

ADX-629 will be supplied as 250 mg tablets for oral delivery.

Drug/biologic name: ADX-629

Active ingredient: ADX-629

### **6.2 Instructions for Use and Administration**

Subject kits will contain bottles containing tablets of test article. The first dose will be taken at the clinic on Day 1. Note: If subject's Day 1 visit is in the evening (i.e., later in the day), and the subject is unlikely to have at least an 8-hour separation between the dose taken at the clinic and the second Day 1 dose, then the dose taken at the clinic will be considered their evening dose and the subject will not dose again until the following morning. Subjects will be instructed to take 1 tablet by mouth twice daily for 12 weeks, once in the morning and once in the evening, with at least 8 hours and preferably 12 hours between doses. Each subject will be provided with a Subject Instruction Sheet providing further dosing details (see Appendix 2).

**For Visit 4**, the morning dose of test article may be taken by the subject at home or may be taken at the site under supervision of the site staff. One day prior to the visit, the site staff will contact the subject to remind them that if the subject chooses to take the morning dose of test article at home on the day of their clinic visit, the subject should: 1) take the morning dose of test article approximately 2 hours prior to the study visit AND 2) note the time of dosing on the Subject Instruction Sheet. Subject will also be informed that if the subject chooses to take the morning dose of test article in the clinic, the subject will need to remain in the clinic for 2 hours after dosing. Time of dosing will be recorded, such that time (in minutes) from test article dosing to blood draw for blood biomarker analysis and urine draw for drug metabolism analysis can be calculated.

**For Visit 5 and Visit 6**, the morning dose of test article may be taken by the subject at home or may be taken at the site under supervision of the site staff. One day prior to the visit, the site staff will contact the subject to remind them to note the time of dosing in the Subject Instruction Sheet if the subject chooses to take the morning dose of test article on the day of their clinic visit at home and to inform them that if the subject chooses to take the morning dose of test article in the clinic, the subject will need to remain in the clinic for 1 hour after dosing. Time of dosing will be recorded, such that time (in minutes) from test article dosing to blood draw for blood biomarker analysis can be calculated.

Subjects will be instructed to bring all test article bottles (used and unused) to each trial visit. At each visit, tablets will be counted.

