--	--

	
tests (chemistry, hematology) and urine samples will be taken for urinalysis and a UPT (for WOCBP). Subject will be reminded to continue to take 1 tablet twice daily until the next clinic visit. AEs will be recorded. The subject will be scheduled for the next visit, as appropriate.
 
Visit 6 (Day 85 ± 3): Week 12/End of Treatment [EOT]. One day prior to the visit, the site staff will contact the subject to remind them to note the time of dosing on the Subject Instruction Sheet if the subject chooses to take the morning dose of test article on the day of their clinic visit at home and to inform them that if the subject chooses to take the morning dose of test article in the clinic, the subject will need to remain in the clinic for 1 hour after dosing.
 
On the day of the visit, the subject will return to the clinic and be queried for any changes in health status since the previous visit, including concomitant medications and concurrent procedures/therapies. Vital signs will be measured. Subject evaluation (PGIC) will be performed by the subject and clinical evaluations (IGA first, then BSA and PASI) will be performed by the investigator. A targeted physical examination based on subject symptoms and an ECG will be performed. Non-invasive skin samples will be collected from non-lesional (perilesional) and lesional skin (same areas collected at baseline). Test article accountability will be documented and all test articles will be collected. Subjects who did not take their morning dose at home will take the morning dose of test article under supervision of study staff and will wait 1 hour before blood sample collection. Time of dosing will be recorded. Blood samples will be taken for biomarker analysis and clinical laboratory tests (chemistry, hematology) and urine samples will be taken for urinalysis and a UPT (for WOCBP). AEs will be recorded. The subject will be scheduled for the End of Study (EOS) phone call follow-up visit 3 days after this visit.
 
Visit 7 (3 days after EOT Visit): EOS. The investigator or designee will call and query the subject for any changes in health status since the previous visit, including concomitant medications and concurrent procedures/therapies, and document any AEs. The subject will exit the study.

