### 9.6 Visit 6 (Day 85 ± 3): Week 12/End of Treatment

**One day prior to the visit, the site staff will contact the subject to remind them to note the time of dosing in the Subject Instruction Sheet if the subject chooses to take the morning dose of test article on the day of their clinic visit at home and to inform them**

**that if the subject chooses to take the morning dose of test article in the clinic, the subject will need to remain in the clinic for 1 hour after dosing.**

*At this visit, the investigator or designee will:*

- Query the subject for any changes in health status since the previous visit, including concomitant medications and concurrent procedures/therapies, and document the findings.
- Measure vital signs (see Section 10.7.1).
- Have the subject perform the subject evaluation (PGIC). See Section 10.6.
- Perform clinical evaluations (IGA first, then BSA and PASI). See Section 10.3, Section 10.5, and Section 10.4, respectively.
- Perform a targeted physical exam (see Section 10.7.2). Record any new or worsening clinically significant abnormalities as AEs.
- Perform ECG (see Section 10.7.3).
- From the same areas collected at baseline, collect non-invasive skin samples from lesional and non-lesional (perilesional to the lesional sample) skin (see Section 12.2).
- Document Test Article Accountability; all test articles will be collected and tablets will be counted.
- If the subject chose to take the test article in the clinic, administer the morning dose of test article to the subject.
- Record dosing time. Note: dosing time can be obtained verbally from the subject, from the Subject Instruction Sheet, or from administration in the clinic.
- Collect blood for blood biomarker analysis (RASP ELISAs and cytokines) **no earlier than 1 hour after** test article administration (see Section 12.3).
- Collect blood and urine samples for clinical laboratory tests (chemistry, hematology, and urinalysis). If possible, subjects should be fasting for approximately 8 hours.
- Perform a UPT for all WOCBP.
- Document any AEs.
- Schedule the subject for a phone call follow-up visit 3 days after this visit.

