##### ***8.6.5 Dosing Compliance***

Subjects will be instructed to take the test article twice daily for 12 weeks so that the expected number of doses will be 168 (or 167 for subjects for whom only the evening dose (after 4PM) is taken on Day 1). Dosing compliance (percent of expected doses) =  $100 \times [(reported\ number\ of\ doses) / (expected\ number\ of\ doses)]$ . Reported number of doses will be calculated from the difference between the number of pills in the bottle dispensed and collected. Compliance will be reported as unknown for any subjects who do not return any study drug bottles. Descriptive statistics will be provided for dosing compliance.

Subjects who take at least 80% of the expected total number of doses and have no other evidence of material dosing non-compliance will be considered to be compliant with test article dosing. The number and percent of compliant subjects will be presented.

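### The SAP's fixed 168 (or 167) expected doses does not match a schedule that doses through the morning of Visit 6, so compliance can be misclassified near the 80% cut-off

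*Protocol*

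**What the plan says.** Two descriptions of the end of dosing stand in the current text.

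**A fixed 12-week course.** In Protocol Section 6.2, "The first dose will be taken at the clinic on Day 1" and "Subjects will be instructed to take 1 tablet by mouth twice daily for 12 weeks". SAP Section 8.6.5 converts this to a number: "twice daily for 12 weeks so that the expected number of doses will be 168". It lowers the figure by one, to 167, when Day 1 holds a single evening dose. The evening exception follows Section 6.2, where after a late Day 1 visit "the dose taken at the clinic will be considered their evening dose and the subject will not dose again until the following morning".

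**Dosing until Visit 6.** The synopsis entry for Visit 5 states: "Subject will be reminded to continue to take 1 tablet twice daily until the next clinic visit". The next clinic visit is Visit 6, on Day 85 ± 3. Section 6.2 also allows the Visit 6 morning dose to be taken at home or at the site. Section 9.6 has site staff call the day before about that dose, and it includes the step "If the subject chose to take the test article in the clinic, administer the morning dose of test article to the subject". All remaining tablets are collected at that visit.

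**Where the count is used.** SAP Section 8.6.5 divides the reported doses, taken from tablet counts, by the expected doses. A subject at 80% or more, with no other evidence of material non-compliance, is classed as compliant. The SAP reports the number and percent of compliant subjects. The denominator does not depend on the date of Visit 6.

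**The concern.** The compliance percentage is meant to compare what a subject took with what the subject was told to take. The numerator runs to whatever day Visit 6 falls on. The denominator stops at Day 84 for everyone. Two subjects who follow every instruction can therefore get different scores, and some score above 100%, only because of where Visit 6 fell in its permitted window.

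What is at stake is the reported compliance percentage and the compliant or non-compliant label for subjects close to 80%. With about 10 subjects, one changed label moves the reported percent compliant by about 10 points (1/10).

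**Working it through.** **Inputs.** Twice-daily dosing for 12 weeks from Day 1 (Protocol 6.2); 168 or 167 expected doses and the 80% rule (SAP 8.6.5); Visit 6 on Days 82 to 88, with a morning dose that day (Protocol 6.2, 9.6 and the synopsis).

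**The SAP's own figures.** 12 × 7 × 2 = 168, and 168 − 1 = 167 for an evening start. Both reproduce exactly. With two doses on Day 1, 168/2 = 84, so the last dose is on the evening of Day 84. With one dose on Day 1, 1 + 166/2 = 84, the same evening.

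**Doses under the visit schedule.** For Visit 6 on day D, there are two doses on each of the D − 1 earlier days and one on the morning of the visit: 2(D − 1) + 1. An evening start gives one fewer.

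**Cut-off.** 0.80 × 168 = 134.4, so 135 doses are needed. For an evening start, 0.80 × 167 = 133.6, so 134 are needed.

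Results for a subject with two doses on Day 1:

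| Visit 6 day | Scheduled doses | Full adherence, % of 168 | 135 doses as % of scheduled | Smallest count that is 80% of scheduled |
|---|---|---|---|---|
| 82 | 163 | 97.0 | 82.8 | 131 (0.80 × 163 = 130.4) |
| 85 | 169 | 100.6 | 79.9 | 136 (0.80 × 169 = 135.2) |
| 88 | 175 | 104.2 | 77.1 | 140 (0.80 × 175 = 140.0) |

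For an evening start the scheduled doses are 162, 168 and 174. Against 167 these also give 97.0%, 100.6% and 104.2%. The 134-dose cut-off is 134/162 = 82.7% of scheduled doses at Day 82 and 134/174 = 77.0% at Day 88.

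**Who is misclassified (two doses on Day 1).**
- Visit 6 on Day 82: 131 to 134 doses is 80.4% to 82.2% of the 163 scheduled, but is scored below 80% (78.0% to 79.8% of 168).
- Visit 6 on Day 85: only a count of exactly 135 changes class.
- Visit 6 on Day 88: 135 to 139 doses is 77.1% to 79.4% of the 175 scheduled, but is scored compliant.

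**The case against.** The best defence is that 12 weeks is a nominal label. The synopsis gives treatment duration as approximately 12 weeks, Visit 6 is titled Week 12/End of Treatment, and any ±3-day window spreads the dose count. The Safety population is the only analysis population, so compliance status removes nobody from any analysis. The text of the Subject Instruction Sheet and the Schedule of Events is not available here, and either may state a last-dose rule. All of this stands, and it keeps the point small. It does not rescue the SAP figure: a window explains why the count varies, but the SAP divides by an exact number that ignores the window and is one short even on the target day.

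A reader might infer something stronger: that subjects reach Visit 6 off drug, so that the Week 12 blood biomarkers mix post-dose and washed-out samples, and even the primary PASI change is affected. The documents do not support this.
- Section 6.2 itself, the Visit 5 reminder, the call the day before and the supervised clinic dose all provide for a dose on the day of Visit 6.
- Even if dosing stopped on the evening of Day 84, the morning of Day 85 is about 12 hours later. That is the preferred dosing interval in Section 6.2, so such a sample would be an ordinary pre-dose trough.
- Nothing visible links a missed dose to the size of a PASI change.
- SAP Section 8.8.10 on blood biomarkers is redacted, so no gap in its handling of draw times can be claimed.

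**Conclusion.** The point holds as a mismatch between a stated figure and the visit schedule. The SAP expects 168 or 167 doses. Dosing to Visit 6 gives 163 to 175, or 162 to 174 after an evening start. Full adherence is scored from 97.0% to 104.2%, and the nominal 80% threshold works as anything from 82.8% down to 77.1% of scheduled doses for a morning start. Only subjects within about five doses of the cut-off are affected, and no efficacy or safety summary changes, so the consequence is minor.

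Assumptions: the subject completes to Visit 6 within the window, and the Visit 6 morning tablet is in the reported count. Section 9.6 lists the tablet count before the clinic dose. If a site counts in that order, the reported number is one lower: 162, 168 and 174 for a morning start at Days 82, 85 and 88, or 96.4%, 100.0% and 103.6% of 168. The mismatch then disappears on the target day but remains across the window. How many subjects will fall near 80% cannot be known from the documents.

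**What to change.** Reconcile the 12-week wording in Protocol Section 6.2 with the Visit 5 reminder and the Visit 6 dosing steps in Sections 6.2 and 9.6, so that one end-of-dosing rule applies throughout. Which rule that should be is for the sponsor.

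In SAP Section 8.6.5, replace the fixed 168/167 with a per-subject expected count, derived from the reconciled rule, whether Day 1 had one or two doses, and the actual Visit 6 date. State whether a dose given in clinic at Visit 6 belongs in both the reported and the expected counts.

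The cost is a clarifying sentence in the protocol, one or two sentences in the SAP and a small change to the compliance derivation. It uses data already recorded and needs no extra visits or subjects. No biomarker flag or exclusion is called for on this ground.

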### **6.3      Warnings, Precautions, and Contraindications**

Subjects with a known sensitivity to any of the ingredients in the test article should not participate in ADX-629-PS-001.

In case of accidental ingestion, subjects should contact the investigator immediately.

The effects of the test article in nursing mothers, pregnant women, and their unborn children are unknown. WOCBP must not be pregnant or planning a pregnancy during the trial period.

## **7.      RANDOMIZATION ASSIGNMENT**

Subjects will not be randomized, as ADX-629-PS-001 is an open-label trial.

[figure not shown]
## **8.      PRIOR AND CONCOMITANT THERAPIES**

Current medications/therapies and any medications/therapies taken in the 30 days prior to the start of the trial (Visit 1/Screening) will be recorded as concomitant medications or concurrent procedures, respectively, with the dose (for medications only) and corresponding indication. The medications to be recorded include prescription and over-the-counter (OTC) medications; vitamins, minerals, and herbal, holistic, and dietary supplements will only be recorded as concomitant medications if being taken for a therapeutic indication. All medications taken on a regular basis must be recorded on the electronic case report forms (eCRFs). All concomitant medications will be coded with the current version of the WHO Drug Dictionary. Therapies to be recorded include any non-drug therapy used to treat a medical condition. Procedures which occurred prior to Visit 2/Baseline will be recorded as Medical History.

Any changes in concomitant medications and/or procedures/therapies during the trial must be recorded. The reason for any changes in concomitant medications and/or therapies should be reported and should reflect either a baseline medical condition documented in the medical history or in conjunction with an AE.

### **8.1 Prohibited Medications or Therapies**

Prior to entry into the trial, subjects must not use the medications or procedures/therapies as specified in Section 5.1.2.

A large black rectangular box redacting the list of prohibited medications and therapies specified in Section 5.1.2.

### **8.2 Allowed Medications or Therapies**

Vitamins and mineral supplements are permitted at dosages considered by the investigator as reasonable for maintaining good health and will not be recorded in the eCRFs. Therapies (medication and non-medication therapies) not restricted by the protocol may be used during the trial for the treatment or prevention of disease or to maintain good health. Non-prohibited chronic therapies being used at Visit 1/Screening may be continued, but must be recorded.

Approved bland moisturizers/emollients (as detailed on a list of such products to be provided by the sponsor or their designee) may be used once daily, but must be recorded as a concurrent procedure. Use of bland moisturizers/emollients more than once daily must be approved by written permission of the Medical Monitor.

OTC shampoo products containing selenium sulfide, zinc pyrithione, and/or salicylic acid as active ingredient(s) may be used to help control inflammatory scalp conditions including scalp psoriasis, but must be recorded as a concomitant medication.

## 9. TRIAL PROCEDURES

Specific activities for each trial visit are listed below.

### 9.1 Visit 1 (Day -21 to -3): Screening

*At this visit, the investigator or designee will:*

- Obtain a signed, written informed consent.
- Record demographics.
- Review I/E criteria.
- Record medical history.
- Record prior and/or concomitant medications and concurrent procedures/therapies.
- Measure vital signs (including height and weight). See Section 10.7.1.
- Perform clinical evaluations (IGA first, then BSA and PASI). See Section 10.3, Section 10.5, and Section 10.4, respectively.
- Perform a brief physical exam (see Section 10.7.2). Record abnormalities in medical history.
- Perform ECG (see Section 10.7.3).
- Collect blood sample for serology (i.e., human immunodeficiency virus (HIV), hepatitis B, and hepatitis C).
- Collect blood and urine samples for clinical laboratory tests (chemistry, hematology, and urinalysis). Subjects must be fasting for approximately 8 hours. If fasting samples cannot be collected at the time of other Visit 1/Screening procedures, the subject may return to the clinic for sample collection such that the results of the clinical laboratory tests are available for review prior to Visit 2/Baseline; such testing will still be considered “Visit 1/Screening” labs.
- Perform a UPT for all females. The result must be negative for the subject to be eligible for the trial.
- Schedule the next visit.

### 9.2 Visit 2 (Day 1): Baseline

*Prior to this visit, the investigator or designee will:*

- Review laboratory results to determine if subject is eligible to enroll in the trial.

*At this visit, the investigator or designee will:*

- Query the subject for any changes in health status since the previous visit, including concomitant medications and concurrent procedures/therapies, and document the findings.
- Confirm I/E criteria.
- Review and update medical history, if needed.
- Measure vital signs (see Section 10.7.1).
- Perform clinical evaluations (IGA first, then BSA and PASI). See Section 10.3, Section 10.5, and Section 10.4, respectively.
- Perform a brief physical exam (see Section 10.7.2). Record any findings in medical history.
- Perform ECG (see Section 10.7.3).
- Collect blood for baseline blood biomarker analysis (RASP ELISAs and cytokines) prior to first test article administration (see Section 12.3).
- Collect blood and urine samples for clinical laboratory tests (chemistry, hematology, and urinalysis). If possible, subjects should be fasting for approximately 8 hours.
- Perform a UPT for all WOCBP. The result must be negative for the subject to be enrolled in the trial.
- Identify a lesion area for skin sampling (this location will be used for all subsequent assessments during the study). Collect non-invasive skin samples from lesional and non-lesional (perilesional to the lesional sample) skin (see Section 12.2).  
**Note:** Be sure to capture and document location of collection for future collections.
- Dispense Subject Instruction Sheet.
- Document Test Article Accountability and dispense the test article.
- Supervise the first dose of test article in the clinic.
- Document any AEs.
- Schedule the next visit.

### 9.3 Visit 3 (Day 15 ± 2): Phone Call

*During this phone call, the investigator or designee will:*

- Query the subject for any changes in health status since the previous visit, including concomitant medications and concurrent procedures/therapies, and document the findings.
- Remind the subject to continue to take 1 tablet twice daily until the next clinic visit.
- Discuss any AEs to determine if the subject should return to the study site for an unscheduled visit.

 WOCBP include any female who has experienced menarche or is 10 years of age or older and who has not undergone successful surgical sterilization (hysterectomy, bilateral tubal ligation, salpingectomy, or bilateral oophorectomy at least 26 weeks prior to Visit 2/Baseline) or is not postmenopausal (defined as amenorrhea for at least 1 year in women 50 years of age and older). Post-menopausal status must also be confirmed with FSH test results from Visit 1/Screening.

- Confirm the next visit.

#### 9.4 Visit 4 (Day 29 ± 3): Week 4

**One day prior to the visit, the site staff will contact the subject to remind them that if the subject chooses to take the morning dose of test article at home on the day of their clinic visit, the subject should: 1) take the morning dose of test article approximately 2 hours prior to the study visit AND 2) note the time of dosing on the Subject Instruction Sheet. Subject will also be informed that if the subject chooses to take the morning dose of test article in the clinic, the subject will need to remain in the clinic for 2 hours after dosing.**

*At this visit, the investigator or designee will:*

- Query the subject for any changes in health status since the previous visit, including concomitant medications and concurrent procedures/therapies, and document the findings.
- Measure vital signs (see Section 10.7.1).
- Have the subject perform the subject evaluation (PGIC). See Section 10.6.
- Perform clinical evaluations (IGA first, then BSA and PASI). See Section 10.3, Section 10.5, and Section 10.4, respectively.
- Perform a targeted physical exam (see Section 10.7.2). Record any new or worsening clinically significant abnormalities as AEs.
- Perform ECG (see Section 10.7.3).
- From the same area collected at baseline, collect non-invasive skin sample from lesional skin for subjects (see Section 12.2).
- Review compliance.
- Document Test Article Accountability; all test articles will be collected and tablets will be counted.
- If the subject chose to take the test article in the clinic, administer the morning dose of test article to the subject.
- Record dosing time. Note: dosing time can be obtained verbally from the subject, from the Subject Instruction Sheet, or from administration in the clinic.
- Collect blood for blood biomarker analysis (metabolite analysis, RASP ELISAs, and cytokines) **between 2 and 4 hours after** test article administration (see Section 12.3).
- Collect blood and urine samples for clinical laboratory tests (chemistry, hematology, and urinalysis). If possible, subjects should be fasting for approximately 8 hours.
- Collect urine sample for urine drug metabolism analysis **between 2 and 4 hours after** test article administration (see Section 12.4).
- Perform a UPT for all WOCBP. The result must be negative for the subject to continue dosing with test article.
- Document any AEs.

- Schedule the next visit.

### 9.5 Visit 5 (Day 57 ± 3): Week 8

**One day prior to the visit, the site staff will contact the subject to remind them to note the time of dosing in the Subject Instruction Sheet if the subject chooses to take the morning dose of test article on the day of their clinic visit at home and to inform them that if the subject chooses to take the morning dose of test article in the clinic, the subject will need to remain in the clinic for 1 hour after dosing.**

*At this visit, the investigator or designee will:*

- Query the subject for any changes in health status since the previous visit, including concomitant medications and concurrent procedures/therapies, and document the findings.
- Measure vital signs (see Section 10.7.1).
- Have the subject perform the subject evaluation (PGIC). See Section 10.6.
- Perform clinical evaluations (IGA first, then BSA and PASI). See Section 10.3, Section 10.5, and Section 10.4, respectively.
- Perform a targeted physical exam (see Section 10.7.2). Record any new or worsening clinically significant abnormalities as AEs.
- Perform ECG (see Section 10.7.3).
- Review compliance.
- Document Test Article Accountability; all test articles will be collected and tablets will be counted.
- If the subject chose to take the test article in the clinic, administer the morning dose of test article to the subject.
- Record dosing time. Note: dosing time can be obtained verbally from the subject, from the Subject Instruction Sheet, or from administration in the clinic.
- Collect blood for blood biomarker analysis (RASP ELISAs and cytokines) **no earlier than 1 hour after** test article administration (see Section 12.3).
- Collect blood and urine samples for clinical laboratory tests (chemistry, hematology, and urinalysis). If possible, subjects should be fasting for approximately 8 hours.
- Perform a UPT for all WOCBP. The result must be negative for the subject to continue dosing with test article.
- Document any AEs.
- Schedule the next visit.

